#### 6.2.2.4 Overall Survival

Separately for injected tumors and overall (per RECIST v1.1), overall survival (OS) is defined as time from first intratumoral injection to date of death for any cause, and is calculated, in months, as:

(Date of death or censoring - date of first intratumoral injection + 1) / 30.4375.

Participants still alive as of the data cut-off date will be censored on the last known alive date from mortality status follow up. For participants that are lost to follow up, the last visit in the database or last contact date where the participant is documented to be alive will be used to estimate last known date alive.

OS will be analyzed based on the Kaplan-Meier methods described for PFS.

#### 6.2.2.5 Duration of Response

Separately for injected tumors and overall (per RECIST v1.1), for participants who have been identified as a responder (achieved an overall response of CR or PR during the PFS observation period, i.e., until any PFS event or censoring), duration of response (DOR) is defined as time from first documentation of CR or PR until disease progression or death for any cause, whichever occurs first, and is calculated, in months, as:

(Date of PD or death - date of first response + 1) / 30.4375.

Censoring algorithms analogous to those for PFS will be used for DOR. If sample size permits, DOR will be analyzed based on the Kaplan-Meier methods described for PFS.

### 6.2.3 Exploratory Efficacy Endpoints and Analyses

Not Applicable.

#### 6.2.4 Multiplicity

No multiplicity adjustments will be performed for multiple analyses or multiple endpoints.

### 6.3 Interim Analysis

No interim analysis will be performed.

### 6.4 Subgroup Analyses

No subgroup analyses are planned.

## 6.5 Correlative/Special Studies

Correlative/special studies, as described in protocol section 8., are outside of the scope of this SAP.

## 6.6 Safety

The primary endpoint of the study is safety which will be assessed on clinical examination and measurement of laboratory parameters.

All participants who receive a dose of Ad/PNP-F-araAMP will be included in the safety analysis population. Each participant will be followed for safety for ~ 60 days following their final study dose. All safety assessments including adverse events, clinical laboratory evaluations, and vital signs will be summarized with descriptive statistics, where appropriate, and listed in the data listings using Medical Dictionary for Regulatory Activities (MedDRA) terms.

Protocol section 12.2 states consideration of the repeat administration of Ad/PNP-F-araAMP as safe if the one-sided 80% upper confidence limit of the percentage of participants in the safety population experience treatment-related Serious Adverse Events as defined in Protocol section 7.2. For example, if 2 of 10 participants experience a treatment related SAE, then the one-sided 80% upper confidence limit is 38.1% and the repeat administration of Ad/PNP-F-araAMP would be considered safe. However, evaluations of the investigational product's (potential) safety profile will not be considered strictly using only assessment of that criterion, but rather will involve broader considerations in addition to assessment of that criterion.

All safety analysis reporting will be based on the Safety Population.

### 6.6.1 Adverse Events

An adverse event (AE) is any unfavorable and unintended diagnosis, symptom, sign (including an abnormal laboratory finding), syndrome or disease which either occurs during the study, having been absent at baseline, or, if present at baseline, appears to worsen. For this study, only abnormal laboratory findings with clinical significance as determined by the PI are considered AEs. AEs will be recorded from the date of informed consent through the study follow-up period (~ 60 days after last dose of study drug). AEs will be assessed for severity, using the NCI-CTCAE version 5.0, relationship to study treatment, relationship to non-study treatment, and seriousness. Relationship assessments of possibly related or greater are defined to be related. Any missing relationship assessments will be assumed to be related, and any missing severity assessments will be assumed to be Severe/Grade 3. Disease progression is not an AE (non-serious or serious), although signs and symptoms thereof may be reportable as AEs.

A treatment-emergent adverse event (TEAE) is defined as an AE with onset occurring at any time point after the first intratumoral administration of Ad/PNP. A TEAE also may be a continuing AE reported prior to the date of the first dose of study drug, which worsens in severity after the first administration of Ad/PNP.

A serious adverse event (SAE) is defined as any adverse experience that suggests a significant hazard, contraindication, side effect, or untoward medical occurrence that:

- Results in death,

- Is life-threatening (Note: the term “life-threatening” refers to an event in which the participant was at risk of death at the time of the event rather than to an event which hypothetically might have caused death if it were more severe.),
- Requires (or prolongs) hospitalization,
- Causes persistent or significant disability/incapacity,
- Results in congenital anomalies or birth defects, or
- Important Medical Event Requiring Medical or Surgical Intervention to Prevent Serious Outcome.

An overview of TEAEs will be produced, including counts and percentages of participants with any incidences of: TEAEs, TEAEs related to study treatment, TEAEs related to non-study treatment, TEAEs related to study treatment or non-study treatment, TEAEs of grade 3 or greater, related TEAEs of grade 3 or greater, TEAEs that are dose limiting toxicities (DLTs), serious adverse events (SAEs), TEAEs leading to study treatment discontinuation, and fatal SAEs.

Adverse events will be coded based on the Medical Dictionary for Regulatory Affairs (MedDRA) version 21.0 for reporting by system organ class (SOC) and preferred term in descending order of overall incidence.

Summaries of adverse events by SOC and preferred term will include the following types:

- TEAEs;
- TEAEs related to study treatment;
- TEAEs related to non-study treatment;
- TEAEs related to study treatment or non-study treatment;
- TEAEs by maximum CTCAE Grade;
- TEAEs with CTCAE Grade 3 or greater;
- TEAEs with CTCAE Grade 3 or greater related to study treatment;
- DLTs;
- SAEs; and
- TEAEs leading to study treatment discontinuation.

When calculating the incidence of AEs, each AE will be counted only once for a given participant within a MedDRA category (e.g., overall, system organ class, or preferred term). When AEs are summarized within levels of another AE assessment (e.g., relatedness or severity), AEs will be counted once per participant at the worst level of the assessment (e.g., strongest relationship to study treatment or greatest severity).

A comprehensive listing of all AEs will be provided in a by-participant data listing. In addition, the following by-participant data listings will be provided:

- SAEs;
- TEAEs related to study treatment or non-study treatment;
- TEAEs leading to study treatment discontinuation; and
- Fatal AEs.

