4.4 Expected Adverse Events

Local injection site reactions have been reported in clinical studies evaluating other non-replicating adenoviral vectors injected intratumorally. The Phase 1 study evaluated two dose levels of Ad/PNP (10^{11} VP/dose in Cohorts 1-3 and approximately 10^{12} VP/dose in Cohort 4) and 3 dose levels of F-araAMP (5, 15, and 25 mg/m^2 in Cohorts 1, 2, and 3, respectively and 25 mg/m^2 in Cohort 4). Among the 12 subjects in the study, the most frequently reported TEAEs were injection site pain (11 subjects, 91.7%) and fatigue (8 subjects, 66.7%). Injection site pain was reported in all but 1 subject receiving 10^{11} VP/dose + 15 mg/m^2 F-araAMP. The event was assessed as treatment-related in 10 subjects (83.3%); most reports were Grade 1 or 2 in severity. All Grade ≥ 3 events in our Phase I study were assessed as unrelated to study treatment, with the exception of 1 report of injection site pain as noted in this section. One subject receiving 10^{12} VP/dose experienced severe (Grade 3) injection site pain on Day 1 that was assessed as definitely related to Ad/PNP injection. The subject went on to complete the study receiving lidocaine injection prior to injection of Ad/PNP. Other injection site reactions included injection site discharge (4 subjects receiving either 10^{11} or 10^{12} VP/dose, 33.3%); injection site erythema, hemorrhage, and pruritus (2 subjects each receiving 10^{11} VP/dose, 16.7%), and injection site paresthesia (1 subject receiving 10^{12} VP/dose, 8.3%). All of these events were reported in only 1 subject within a cohort and all were assessed as Grade 1 or 2 in severity; most were reported as treatment-related.

F-araAMP is a purine analog used to treat patients with chronic lymphocytic leukemia (CLL). Besides being an anti-tumor agent against lymphoid malignancies, F-araAMP has immunosuppressant activity and is incorporated in preparatory regimens for allogeneic bone marrow transplantation.

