12.3 Adverse Events

All AEs will be coded by system organ class (SOC) and preferred term using MedDRA v25.0.

Summary tables for treatment emergent adverse events will include number of occurrences of events by SOC, and numbers and percentages of subjects experiencing adverse events by SOC and preferred term. If a subject has more than one AE which codes to the same preferred term, the subject will be counted only once for that preferred term. Similarly, if a subject has more than one AE within an SOC category, the subject will be counted only once in that SOC category. Summary tables to be generated include: summary of AEs, relationship of AEs to study drug, severity of AEs, AEs leading to study drug discontinuation and serious AEs. Data listings will be provided for AEs, AEs leading to study drug discontinuation, and serious AEs.

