### 1.1 Changes to the Planned Analysis

Additional details may have been provided for analyses and data presentations described in the protocol, but no changes were made to analyses specified in the protocol. Any deviations from the approved statistical analysis plan will be described and justified in the final clinical study report.

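### SAP 6.6.1 leaves out the count of TEAE occurrences by SOC that Protocol 12.3 promises, SAP 1.1 declares no change, and neither document plans an AE summary by cycle

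*SAP*

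**What the plan says.** Protocol 12.3 (Adverse Events) sets out two kinds of TEAE summary. One counts events: "Summary tables for treatment emergent adverse events will include number of occurrences of events by SOC". The other counts people, by SOC and preferred term. For a subject with several AEs under one preferred term, "the subject will be counted only once for that preferred term", and the same applies within an SOC.

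SAP 6.6.1 (Adverse Events) specifies participant-level summaries throughout:

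- The overview gives "counts and percentages of participants with any incidences of" a list of event types.
- For incidence by SOC and preferred term, "each AE will be counted only once for a given participant within a MedDRA category".
- For tables split by relatedness or severity, "AEs will be counted once per participant at the worst level of the assessment". One of these tables is "TEAEs by maximum CTCAE Grade".
- Every AE also goes into a by-participant listing.

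No event count and no AE table by cycle is described in the SAP. SAP 1.1 (Changes to the Planned Analysis) says that "no changes were made to analyses specified in the protocol". SAP 2 gives the primary endpoint as safety with repeat cycles, measured by AEs and laboratory parameters.

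**The concern.** Repetition is the new safety question in this trial. Protocol 2.4 describes Phase 1 as a single administration, and Protocol 4.4 says that the toxicity of intratumorally generated F-Ade with repeat injection is not known. Here a participant may have up to 3 × 5 = 15 Ad/PNP administrations and 15 F-araAMP infusions. Protocol 7.5.3 lets the Safety Monitoring Committee act on the frequency of AEs as well as their type. SAP 6.6 says that the safety judgment will draw on more than the numeric SAE criterion, so the AE tables carry weight.

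A participant-level table records whether a term ever occurred. It reads the same for one episode as for an episode in every cycle. The occurrence count in Protocol 12.3 is the only planned AE summary that would separate the two. Without it, a reader of the study report would have to reconstruct recurrence from the listing, and SAP 1.1 would not tell that reader that a protocol-specified summary was missing.

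**Working it through.** **1. The plan's own safety figure.** The only numeric safety criterion counts participants with a treatment-related SAE. The exact (Clopper-Pearson) one-sided 80% upper limit for x of n is the 0.80 quantile of a Beta(x + 1, n − x) distribution. For 2 of 10 this is Beta(3, 8), which gives 0.38094. That matches the tables in Protocol 12.1 and SAP 3.3 and the 38.1% in Protocol 12.2 and SAP 6.6. All 11 rows of the table agree to within 0.0001. Because the criterion counts participants, adding event counts does not affect it.

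**2. The two documents side by side.**

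| Summary | Protocol 12.3 | SAP 6.6.1 |
|---|---|---|
| Participants, n (%), by SOC and preferred term, each counted once | Yes | Yes |
| Number of TEAE occurrences by SOC | Yes | Not mentioned |
| Number of TEAE occurrences by preferred term | No | No |
| TEAEs by cycle | No | No |
| Worst severity per participant | Severity table planned | Yes, maximum grade |
| AEs leading to discontinuation | Yes | Yes |
| Listing of all AEs | Yes | Yes |

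The second row is the discrepancy. The fourth row is a gap that both documents share.

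**3. What each count can show.** The data below are assumed: 10 participants, all treated in all 5 cycles, one AE term, and one episode per affected participant per cycle.

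| Pattern | Events in cycles 1 to 5 | Participants ever affected (SAP) | Occurrences (Protocol) |
|---|---|---|---|
| A: 3 participants, cycle 1 only | 3, 0, 0, 0, 0 | 3/10 (30%) | 3 |
| B: the same 3, every cycle | 3, 3, 3, 3, 3 | 3/10 (30%) | 3 × 5 = 15 |
| C: rising | 1, 2, 3, 4, 5 | 5/10 (50%) | 15 |
| D: falling | 5, 4, 3, 2, 1 | 5/10 (50%) | 15 |

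A and B look the same under the SAP, and the occurrence count separates them. C and D look the same under both counts. A pooled rate does not help either: with 10 × 5 = 50 participant-cycles, C and D both give 15/50 = 0.30 events per cycle. Only a table by cycle separates them, reading 10%, 20%, 30%, 40%, 50% for C and the reverse for D.

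**4. Room left in participant incidence.** Protocol 4.4 reports injection site pain in 11 of 12 Phase 1 subjects (91.7%). If incidence here were similar, it could rise by at most 100 − 91.7 = 8.3 points however often the event recurred. The room is larger for treatment-related injection site pain (100 − 83.3 = 16.7 points) and for fatigue (100 − 66.7 = 33.3 points).

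**The case against.** The strongest objection is that the omission is inferred from silence. The SAP is to be read with the protocol, its mock shells are kept in a separate document, and its counting rule is introduced as applying to incidence. SAP 1.1 could mean that Protocol 12.3 still applies in full. This is possible, and the shells may contain the count. But SAP 6.6.1 lists its AE summaries in detail and this one is not among them, so the text should settle the matter.

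A reader might infer several stronger things that the documents do not support:

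- *That the once-per-participant rule contradicts the protocol.* It does not, because Protocol 12.3 has the same rule for incidence.
- *That cumulative toxicity cannot show in any primary safety table.* Laboratory parameters are part of the primary endpoint, and SAP 6.6.2 summarizes hematology and chemistry at each time point with change from baseline. Worsening to a higher grade moves the maximum-grade table, though without its timing. Toxicity that ends treatment appears in the discontinuation table. With 10 to 20 participants, the AE listing can be read by hand.
- *That the SAP caused the loss of information on build-up.* The protocol promises occurrences by SOC only, with no breakdown by cycle. An SOC total pools its terms, so it would not isolate injection site pain.
- *That the 8.3 points is a forecast for this trial.* The Phase 1 figure pools four cohorts, two vector dose levels and 2 melanoma subjects, with 0.5 ml injections against volumes up to 5 ml here. It only illustrates how a ceiling works.

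The other outputs compensate only in part. Laboratory tables cannot show injection site pain or fatigue, the two most frequent Phase 1 TEAEs. Protocol 4.3 limits DLTs to 28 days from the start of Cycle 1 dosing, so that table is uninformative about later cycles. A listing is also not the summary table that Protocol 12.3 promised.

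**Conclusion.** The point holds in a limited form. SAP 6.6.1 does not specify the TEAE occurrence count by SOC that Protocol 12.3 promises, and SAP 1.1 reports no change. As the SAP stands, repeat episodes of the same term in one participant appear only in listings. Separately, neither document plans an AE summary by cycle, which is a weakness when the primary endpoint is safety with repeat cycles.

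In the assumed example, a fivefold difference in episodes (3 against 15) leaves the SAP table at 30%. The effect in real data depends on how often events recur, which the documents do not give. The SAE criterion and its 38.1% for 2 of 10 stand. The conclusion assumes that the mock shells, which are not part of the documents, do not already supply the count.

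**What to change.** In SAP 6.6.1:

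1. Restore the number of TEAE occurrences by SOC beside n (%). Giving it by preferred term as well would be an improvement beyond Protocol 12.3, and is needed to isolate a term such as injection site pain.
2. Add a TEAE table by cycle of onset, for all, related, and Grade 3 or greater events, with the number of participants treated in each cycle as the denominator. State how events with onset in follow-up after the last cycle are assigned. This table is also an addition to the protocol.
3. If the occurrence count is not restored, correct SAP 1.1 to declare and justify the omission.

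The cost is a little more table programming. Onset dates are recorded under Protocol 7.5.1, and cycles and administrations are already summarized under SAP 6.1.7.

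Two cautions belong with the tables. Event counts depend on how sites separate a recurrent episode from a continuing one, and Protocol 7.5.1 gives no rule for this, so the by-cycle participant count should be read alongside them. Later cycles include only participants who stayed on treatment, so a falling rate over cycles may reflect who remained.

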## 6.6.2 Clinical Laboratory Evaluations

Clinical laboratory tests (including hematology, serum chemistry, coagulation, CD4/CD8 T-Cell Subsets, and urinalysis) will be performed at local laboratory facilities at each site, at visits per the Protocol Study Procedures Table (Appendix 2). Hematology and serum chemistry test values will be converted as required to values based on the International System of Units (SI). All summaries and listings will use SI units.

The following laboratory tests will be reported in data summaries:

Hematology: hematocrit, hemoglobin, platelet count, RBC, and WBC, MCH, MCHC, MCV, neutrophils (absolute), eosinophils (absolute), basophils (absolute), lymphocytes (absolute), and monocytes (absolute). Percentage differentials of neutrophils, eosinophils, basophils, lymphocytes, and monocytes.

Serum chemistry: sodium, potassium, carbon dioxide, chloride, glucose, magnesium, calcium, blood urea nitrogen (BUN), creatinine (Cr), phosphorus, albumin, alkaline phosphatase, ALT, AST, total bilirubin, total protein.

Coagulation: PT, INR, aPTT.

CD4/CD8 T-Cell Subsets: CD4/CD8 T-cell.

Urinalysis: pH, specific gravity, Leukocyte esterase (Leukocytes), Nitrite, Urobilinogen, Protein, Phosphorus, Occult blood (Hemoglobin & erythrocytes), Ketones, Bilirubin, Glucose.

Pregnancy: serum/urine pregnancy test.

Results of laboratory tests from hematology and chemistry evaluations that are outside of the reference range will be flagged and displayed in the summary tables. Descriptive statistics (e.g., number of participants, mean, STD, median, Q1, Q3, minimum, and maximum) for hematology and serum chemistry measurements will be calculated for each time point. The same descriptive statistics will be generated for these changes from baseline for each measurement. For the selected laboratory tests identified in section 6.1.3, a spaghetti plot will visually track measurements over time for each participant. Baseline is defined as the last measurable value prior to dosing on Day 1. All clinical laboratory data will be provided in data listings, with values outside of the reference range flagged. No grading of laboratory tests results will be performed.

## 6.6.3 Vital Signs

Vital signs include: pulse rate (bpm), respiratory rate (bpm), temperature (°C), systolic and diastolic blood pressure (mmHg). Observed values and changes from baseline for these vital signs will be summarized at each visit and time point.

Vital signs will be provided in a by-participant data listing.

#### 6.6.4 ECOG Performance Status

ECOG data will be summarized by score categories 0-4 at scheduled visits with frequency count and percent. Percentages will be based on the number of non-missing observations. In addition, a shift table of baseline to the last visit will be provided. ECOG data will be provided in a by-participant data listing.

#### 6.6.5 Electrocardiogram (ECG)

Electrocardiogram (ECG) parameters include: HR, PR, QT, QTcF. Observed values and changes from baseline for ECG parameters will be summarized at each visit and time point.

ECG data will be provided in a by-participant data listing.

#### 6.6.6 Physical Examinations

Physical examination results will be presented in a by-participant data listing.

## 8 APPENDICES

### 8.1 APPENDIX 1: Partial Date Conventions

#### ALGORITHM FOR TREATMENT EMERGENCE OF ADVERSE EVENTS:

START DATE	STOP DATE	ACTION
Known	Known/Partial/ Missing	If start date < study treatment start date, then not TEAE If start date >= study treatment start date and < (end of treatment + 60 days), then TEAE If start date > (end of treatment + 60 days), then not TEAE *if time is collected, consider time in determining if event is a TEAE
Partial, but known components show that it cannot be on or after study treatment start date	Known/Partial/ Missing	Not TEAE
Partial, could be on or after study treatment start date	Known	If stop date < study treatment start date, then not TEAE If stop date >= study treatment start date, then TEAE *if time is collected, consider time in determining if event is a TEAE
	Partial	Impute stop date as latest possible date (i.e., last day of month if day unknown or 31st December if day and month are unknown), then: If stop date < study treatment start date, then not TEAE If stop date >= study treatment start date, then TEAE
	Missing or ongoing is checked	Assumed TEAE
Missing	Known	If stop date < study treatment start date, then not TEAE If stop date >= study treatment start date, then TEAE *if time is collected, consider time in determining if event is a TEAE
	Partial	Impute stop date as latest possible date (i.e., last day of month if day unknown or 31st December if day and month are unknown), then: If stop date < study treatment start date, then not TEAE If stop date >= study treatment start date, then TEAE
	Missing or ongoing is checked	Assumed TEAE

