7.5 Safety Monitoring and Reporting

7.5.1 Monitoring of Adverse Events

All subjects will be monitored closely for AEs during study participation. Subjects who discontinue prematurely from the study will be encouraged to return for assessment of safety and their physician contacted to obtain follow-up safety information.

The investigator will monitor subjects for the occurrence of AEs throughout their participation in the study and record all observed AEs in the CRF.

Adverse events spontaneously reported by the subject and/or in response to an open question from study personnel or revealed by observation, physical examination, or other diagnostic procedures are to be recorded in the study specific worksheets. Any clinically relevant deterioration in laboratory assessments or other clinical findings, as assessed by the investigator, is considered an adverse event and must be recorded on the appropriate pages of the CRF. Whenever possible, symptoms should be grouped as single syndrome or diagnosis. The investigator should specify the date of onset, maximal intensity, corrective therapy given, outcome, and his/her assessment of causality (i.e., whether the adverse event was related to the study drug) (Section 7.3).

From signing of informed consent through initiation of study treatment, only SAEs considered related to study procedure(s) should be recorded. After initiation of study treatment (Day 1) through Day 56 of the subject's last treatment cycle, all adverse events regardless of seriousness or relationship to study drug should be recorded.

Serious adverse events considered related to prophylactic antibiotic treatment (and not suspected to be related to study treatment) are expected AEs. They should be collected but are not subject to expedited reporting.

Any AE that is not resolved by the end of the study and considered to be potentially related to study drug or was the cause for the subject's withdrawal will be followed as clinically indicated until its resolution, or if non-resolving, until considered stable.

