### 5.3 Data Imputation Rules

Generally, missing data will not be imputed, and will be presented as collected in the study database.

In cases where adverse event or medication dates are missing, the imputation methods described in Appendix 1 will be used to determine flags for treatment-emergent events and concomitant medications.

Conventions for censoring for time-to-event efficacy endpoints are described within the definitions of the endpoints in section 6.2.2.

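### SAP Appendix 1 flags every AE known to start before dosing as not treatment-emergent, with no test for worsening, contrary to the SAP's own TEAE definition

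*SAP*

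**What the plan says.** **Definition.** SAP 6.6.1 counts AEs that begin after the first intratumoral administration and then adds a second limb: "A TEAE also may be a continuing AE reported prior to the date of the first dose of study drug", provided it is one "which worsens in severity after the first administration of Ad/PNP". Protocol 7.1 carries the same two limbs.

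**Flag.** SAP 5.3 says that, where AE or medication dates are missing, "the imputation methods described in Appendix 1 will be used to determine flags for treatment-emergent events and concomitant medications". The table in Appendix 1 opens with a row for known start dates, whatever the state of the stop date: "If start date < study treatment start date, then not TEAE". A second row, headed "Partial, but known components show that it cannot be on or after study treatment start date", also returns a negative flag. No row refers to severity or to a change in grade.

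**Recording before dosing.** The two documents differ. Protocol 7.5.1: "From signing of informed consent through initiation of study treatment, only SAEs considered related to study procedure(s) should be recorded". SAP 6.6.1: "AEs will be recorded from the date of informed consent through the study follow-up period". The procedures tables appear to differ in the same way. The AE row in SAP Appendix 2 is marked at the screening visit, and the one in Protocol 9.1 is not.

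**What is recorded per event.** Protocol 7.5.1 asks for the onset date and the maximal intensity. Neither document says whether a rise in grade opens a new record or updates the existing one.

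**The concern.** Safety is the primary endpoint, and the TEAE flag decides which events enter most of the safety tables. If the flag follows Appendix 1 literally, the second limb of the definition has no effect on any event dated before treatment. SAP 1.1 says that no protocol-specified analysis was changed, yet this rule would narrow the protocol's TEAE definition.

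The protocol's entry criteria allow conditions that could worsen. Exclusion criterion 7 bars baseline neuropathy only above Grade 2, and Section 4.3 makes neurotoxicity above Grade 2 a reason to discontinue treatment. A Grade 2 neuropathy that rose to Grade 3, held on one record with its old onset date, would be absent both from the Grade 3 or greater table and from the table of TEAEs leading to discontinuation.

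The treatment of vague dates sharpens the contrast. Under Appendix 1 an ongoing event with no start date is assumed to be treatment-emergent. A fully dated pre-dose event that worsens is excluded.

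**Working it through.** No sample-size, power or alpha figure depends on this point, so the check compares the two rules case by case.

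**1. The two rules side by side** (known start date; later onset taken within the 60-day window)

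| Case | Definition (SAP 6.6.1, Protocol 7.1) | Appendix 1 | Result |
|---|---|---|---|
| Onset before first dose, no worsening | not TEAE | not TEAE | agree |
| Onset before first dose, worsens after it | TEAE | not TEAE | **conflict** |
| Onset after first dose | TEAE | TEAE | agree |

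The rules part on one case only, and it is the case the second limb of the definition was written for. The row for partial dates that must precede treatment behaves in the same way.

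**2. Does Appendix 1 reach such an event?** A continuing AE has no stop date, so it meets the missing-date condition in SAP 5.3. The known-start row accepts a missing stop date. No section says that 6.6.1 overrides the table.

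**3. Which outputs depend on the flag?** SAP 6.6.1 lists ten summaries by system organ class and preferred term. Eight are worded as TEAEs; the other two are DLTs and SAEs. Most of the overview table and two of the listings are also limited to TEAEs. The comprehensive AE listing, the SAE summary and the SAE listing are not.

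**4. Size per participant.** Incidence is participants with the event divided by N, and the planned safety population is 10 to 20.
- N = 10: 1/10 = 10 percentage points
- N = 20: 1/20 = 5 percentage points

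This applies where the misflagged event is the participant's only one in that category. In the table by maximum grade, a participant with another, milder event in the category would instead move to a lower grade. Overall TEAE incidence can fall but cannot rise.

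**5. Which records are exposed?**
- Worsening entered as a new AE dated after Day 1: flagged TEAE, nothing lost.
- No pre-dose record, so the event is first entered after Day 1 with a post-dose date: flagged TEAE, nothing lost.
- One record that keeps a pre-dose onset and takes the later maximal grade: flagged not TEAE, lost to the TEAE tables.

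Only the third route does harm. The documents neither require it nor rule it out.

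**6. The SAE criterion.** Protocol 12.2 and SAP 6.6 count treatment-related SAEs. Their example of 2 in 10 reproduces as the 0.80 quantile of a Beta(3, 8) distribution, 0.38094, or 38.1%. The criterion is not worded in terms of TEAEs, so the flag does not enter it.

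**The case against.** The strongest reply is that Appendix 1 is titled as a set of partial-date conventions and SAP 5.3 calls on it only for missing dates, so a fully dated AE falls under 6.6.1, worsening limb included. That reading is fair for an event with both dates complete. It does not cover a continuing event with no stop date, and it leaves the known-start row without a clear purpose.

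The second reply is that few records will be exposed. Under the AE definition, a condition present at baseline becomes an AE only when it appears to worsen, so the natural date is that of the worsening. Current illnesses go into the baseline medical history. Protocol 7.5.1 keeps almost all pre-dose events other than procedure-related SAEs out of the AE data, and those SAEs would still reach the SAE table. This stands and limits the consequence. It does not settle the matter, because the SAP records AEs from consent and no section fixes the dating rule.

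Third, the CRF and the protocol clarification letter named in SAP 1 may already say that a rise in grade opens a new record. They are not among the documents reviewed, so the number of events lost cannot be asserted.

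Finally, the SAP is cautious elsewhere: missing relationship counts as related, missing severity as Grade 3, and unresolved dates as treatment-emergent. That is true, but none of those rules applies to a dated event that worsens.

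**Conclusion.** The contradiction is in the current text. Appendix 1 gives the wrong flag for a case that SAP 6.6.1 and Protocol 7.1 expressly define. For each affected participant it lowers TEAE incidence in a category by 10 points at N=10 or 5 points at N=20, if the event keeps its pre-dose onset date and is that participant's only one in the category. The number of such participants is unknown and may be small or zero.

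A reader might infer three stronger things that the documents do not support:
- **That TEAE incidence will be heavily understated.** The documents give no rate of baseline symptoms that worsen, and no share of those recorded under the old onset date, so no total can be estimated.
- **That the events disappear from the report.** They stay in the all-AE listing, and serious ones stay in the SAE table and listing.
- **That the safety criterion is biased.** It rests on treatment-related SAEs and does not use the flag.

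This is a consistency correction to make before database lock.

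**What to change.** - In both pre-treatment rows of Appendix 1, add an exception: if severity increased after the first Ad/PNP administration, the event is a TEAE with onset at the date of worsening.
- Reconcile Protocol 7.5.1 with SAP 6.6.1 and the AE row of SAP Appendix 2, so that one rule governs which AEs are recorded between consent and first dose.
- State in the SAP and the CRF completion notes that worsening of a baseline condition is entered as a new AE dated at the worsening. If the CRF already says so, cite it.
- Before lock, list AE records with a pre-dose onset and query whether the grade rose after dosing.

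The cost is a clause in two table rows, one programming condition, a CRF completion note and a short data query. No change to design, sample size or visits is needed.
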